Clinical Trial Protocol

A Multicenter, Randomized, Double-masked and Placebo-controlled Study
Evaluating the Efficacy and Safety of SI-614 Ophthalmic Solution in Patients
with Dry Eye (The SIDE Study)

Version 1.0 23MAR2022

NCT05411367

Clinical Trial Protocol

Protocol Title: A Multicenter, Randomized, Double-masked and Placebo-controlled Study Evaluating the Efficacy and Safety of SI-614 Ophthalmic Solution in Patients with Dry Eye (The SIDE Study)

Protocol Number: 614/1132

Study Phase: 3

Product Name: SI-614 ophthalmic solution

IND Number: 112,592

Indication: Keratoconjunctivitis sicca (Dry Eye)

Investigators: Multi-Center

Sponsor: Seikagaku Corporation
[name]
[name]

Contract Research Organization: [REDACTED]

IRB: [REDACTED]

Original Protocol: March 23, 2022/Version 1.0

Amendment 1: Not applicable

Confidentiality Statement

This protocol contains confidential, proprietary information of [REDACTED] and/or Seikagaku Corporation. Further dissemination, distribution or copying of this protocol or its contents is strictly prohibited.

MEDICAL MONITOR

[REDACTED]	Responsible for medical management, safety surveillance, confirming patient eligibility, and reviewing safety data and clinical study report
------------	--

SPONSOR PERSONNEL

[REDACTED]	Responsible for supervision of planning, management of clinical trial
[REDACTED]	Responsible for study management

[REDACTED] PERSONNEL

[REDACTED]	Responsible for oversight and coordination of clinical trial and administrative follow-up
[REDACTED]	Responsible for oversight of clinical planning, management and conduct of the clinical trial.
[REDACTED]	Responsible for planning, management, conduct, and monitoring of clinical trial

SYNOPSIS

Protocol Title:	A Multicenter, Randomized, Double-masked and Placebo-controlled Study Evaluating the Efficacy and Safety of SI-614 Ophthalmic Solution in Patients with Dry Eye (The SIDE Study)
Protocol Number:	614/1132
Study Drug:	
• 0.3% SI-614 ophthalmic solution• Placebo (vehicle of SI-614 ophthalmic solution)
Study Phase:	3
Study Objective:	To evaluate the efficacy and safety of 0.3% SI-614 ophthalmic solution compared with placebo when administered 4 times daily for 84 days in patients with dry eye
Overall Study Design	
Structure:	Multi-center, double-masked, randomized, placebo-controlled study
Duration:	2 weeks of run-in period and 12 weeks of treatment period
Controls:	Placebo
Dosage/Dose Regimen:	One drop of study drug will be instilled in each eye 4 times daily (morning, noon, afternoon, evening before bedtime) for 84 days. Patients will be randomized in a 1:1 ratio into one of the 2 arms of the study: 
• 0.3% SI-614• Placebo
Summary of Visit Schedule:	7 visits and 3 phone calls over the course of approximately 14 weeks 
• Visit 1, Day -14 ± 3• Visit 2, Day 1• Visit 3, Day 8 ± 2• Visit 4, Day 15 ± 2• Phone Call for Drug Compliance, Day 22 ± 2• Visit 5, Day 29 ± 3• Phone Call for Drug Compliance, Day 43 ± 2• Visit 6, Day 57 ± 3• Phone Call for Drug Compliance, Day 71 ± 2• Visit 7, Day 85 ± 3

Measures Taken to Reduce Bias:	This is a randomized and double-masked study.
Study Population Characteristics	
Number of Patients:	Approximately 230 (115 per treatment arm) patients will be enrolled at up to 10 sites.
Condition/Disease:	Keratoconjunctivitis sicca (Dry Eye)
Inclusion Criteria:	
Patients must:
 
1. Be male or female of any race, at least 18 years of age at Visit 1.2. Have provided verbal and written informed consent.3. Be able and willing to use eye drops 4 times daily with a compliance rate of 80% or greater during the run-in period and follow instructions, including participation in all study assessments and visits.4. Have a patient-reported history of dry eye in both eyes for at least 6 months prior to Visit 1.5. Have used and/or desired to use an artificial tear substitute for dry eye symptoms within 6 months prior to Visit 1.6. Have a best-corrected visual acuity score of +0.70 logarithm of the minimum angle of resolution (logMAR) or better in both eyes at Visit 1, as assessed by Early Treatment of Diabetic Retinopathy Study (ETDRS) chart.7. Report an average score of 2.0 or higher in at least 1 of the 5 symptoms over the 7 days prior to Visit 2 as measured by the [REDACTED] Ocular Discomfort and 4-Symptom Questionnaire from the patient daily diary8. Have ALL of the following in the qualifying eye(s), [REDACTED] at Visits 1 and 2:
a) A tear film break-up time (TFBUT) of ≤ 5 seconds and ≥ 1 secondb) A fluorescein staining score of ≥ 2 in at least 1 region [REDACTED]

	
c) A conjunctival redness score of ≥ 1 [REDACTED]
 
d) A total lissamine green staining score of ≥ 2 [REDACTED]
 
9. Demonstrate a response to the [REDACTED] at Visits 1 and 2 in the qualifying eye(s), as defined as meeting ALL of the following criteria:
 
Have an increase of ≥ 3 in fluorescein staining score in the cornea [REDACTED]Report a score of ≥ 3 [REDACTED] Ocular Discomfort Scale [REDACTED] 
10. If a female of childbearing potential, have a negative urine pregnancy test at Visit 1 and will be using an adequate method of birth control throughout the study period. [Females are considered of childbearing potential unless they are surgically sterilized (bilateral tubal ligation, hysterectomy or bilateral oophorectomy) or post-menopausal (at least 12 months since last menses). Adequate birth control is defined as use of hormonal contraceptives (oral, implantable, injectable or transdermal), spermicide in conjunction with a barrier such as condom or diaphragm, or an intrauterine device, or surgical sterilization of partner. For non-sexually active females, abstinence may be regarded as an adequate method of birth control; however, if the patient becomes sexually active during the study, she must agree to use adequate birth control as defined above for the remainder of the study.]

Exclusion Criteria:	
Patients must not:
 
Have any clinically significant slit lamp findings at Visit 1 or Visit 2, including active blepharitis, meibomian gland dysfunction, lid margin inflammation or ocular allergies that

	
requires therapeutic treatment and/or, in the opinion of the investigator, may interfere with the study parameters.
 
2. Be diagnosed with an ongoing ocular infection (bacterial, viral or fungal), or active ocular inflammation (eg, follicular conjunctivitis) at Visit 1 or Visit 2.3. Have a history of laser in situ keratomileusis (LASIK) surgery in either eye within 12 months prior to Visit 1, or have any scheduled LASIK surgery during the study period.4. Have had any ocular surgical procedure within 12 months prior to Visit 1, or have any scheduled ocular surgical procedure during the study period.5. Have used contact lenses within 30 days prior to Visit 1 or anticipates use of contact lenses during the study period.6. Have used punctal plugs within 3 months prior to Visit 1 or anticipates use of punctal plugs during the study period.7. Have used nasal spray for dry eye (i.e. TYRVAYA[®]) within 30 days prior to Visit 1 or anticipates use of nasal spray for dry eye during the study period.8. Have used topical ocular cyclosporine (i.e., Restasis[®] or CequaTM) or topical lifitegrast (i.e. Xiidra[®]) within 45 days prior to Visit 1.9. Have used any topical ocular prescription (including medications for glaucoma) or over-the-counter (OTC) solutions, artificial tear substitutes, gels or scrubs within 24 hours prior to Visit 1 or during the study period.10. Be currently using any medication known to cause ocular drying or increased lacrimation that has not been used on a stable dosing regimen for at least 30 days prior to Visit 1, or anticipates a change in such medication during the study period.11. Have a current malignancy or has received treatment of malignancy within the past 5 years prior to Visit 1. Patients who have undergone
--	---

	
successful resection of a basal cell or squamous cell carcinoma of the skin may be enrolled even if the resection was within 5 years.
 
12. Have an uncontrolled systemic disease including, but not limited to clinically significant cardiovascular disease, pulmonary disease, or metabolic disease or any other systemic disease/symptoms that, in the opinion of the investigator, would interfere with study parameters.
 
13. Have an uncontrolled psychiatric condition that required a change in medication in the 30 days prior to Visit 1, or anticipates hospitalization or change in such medication during the study period, or substance or alcohol abuse.
 
14. Be a female who is pregnant, nursing an infant, or planning a pregnancy.
 
15. Have a known allergy and/or sensitivity to the study drug or its components.
 
16. Have a condition or is in a situation that, in the opinion of the investigator, may put the patient at significant risk, may confound the study results, or may interfere significantly with the patients' participation in the study.
 
17. Be currently enrolled in an investigational drug or device study, have used an investigational drug or device within 45 days prior to Visit 1, or have been previously randomized to receive SI-614 ophthalmic solutions or placebo.

--	--

Evaluation Criteria

Efficacy Measures:	
Primary Efficacy Measures:
 
The following primary endpoint will be evaluated:
 
• Change from baseline [REDACTED] in total corneal fluorescein staining score [REDACTED] in the study eye. 
Secondary Efficacy Measures:
 
The following secondary endpoint will be used:
 
• Change from baseline in the average score of ocular discomfort and dryness at the bedtime assessment from the patient daily diary during Day 1 through Day 14.
---------------------------	--

	
Exploratory Efficacy Measures:
 
The following exploratory efficacy measures will be used:
 
Signs
 
• Fluorescein staining score [REDACTED]• Lissamine green staining score [REDACTED]• TFBUT• Conjunctival redness [REDACTED] 
Symptoms
 
• Patient daily diary during dosing period• Ocular Surface Disease Index[©] (OSDI)[©] questionnaire• [REDACTED] Ocular Discomfort and 4-Symptom Questionnaire• [REDACTED] Ocular Discomfort Scale
Safety Measures:	
• Best-corrected visual acuity• Slit lamp biomicroscopy• Adverse event (AE) query
Other Measures:	
• Urine pregnancy test

General Statistical Methods and Types of Analyses
 
Analysis Populations
 
• Intention-to-Treat Population The intention-to-treat (ITT) population includes all randomized patients. Subjects in the ITT population will be analyzed as randomized. The primary analysis will be performed on the ITT population with the primary estimand.• Per-Protocol Population The per-protocol (PP) population is defined as all ITT patients who have no major protocol deviations and completed the trial. Protocol deviations will be assessed prior to database lock and unmasking. The PP population will be analyzed using observed data only for efficacy variables. Subjects in the PP population will be analyzed as treated. 
Safety Population – The safety population will include all patients who receive at least 1 dose of randomized study drug. Subjects in the Safety population will be analyzed as treated.
 
Sample Size
 
Difference and standard deviation (SD) estimates are derived from the Phase 2 and Phase 2/3 study.
	

The primary endpoint is the change from baseline [REDACTED] Day 29 [REDACTED] in total corneal fluorescein staining. The study will be considered successful if and only if this endpoint is met. In order to have 90% power to detect a difference of -0.75 between SI-614 and placebo, 109 patients per treatment arm are required to be randomized. This assumes a two-sided test at alpha = 0.05 and a common SD of 1.7 in both treatment arms.

Accounting for up to 5% dropouts in the study, 115 patients per treatment arm, or 230 total patients are required to have 90% power for the primary endpoint.

The hierarchical, secondary endpoint of the change from baseline in the average score of ocular discomfort and dryness at the bedtime assessment from the patient daily diary during Day 1 through Day 14 will have 51% power with this sample size, assuming a difference between SI-614 and placebo of -0.13. This endpoint will be tested conditional upon the primary endpoint being successful, thereby maintaining the study-wide type I error rate for both endpoints. The sample size calculation assumes a two-sided test at alpha = 0.05 and a common SD of 0.48 in both treatment arms.

Multiplicity

Hierarchical fixed sequence testing will be used in the analysis of the primary dry eye sign endpoint and the secondary dry eye symptom endpoint to maintain study wide type I error. The primary endpoint of change from baseline [REDACTED] at Day 29 [REDACTED] of the corneal total fluorescein staining score will be evaluated at a two-sided study wide alpha level of 0.05. If the primary endpoint is statistically significant, then the secondary endpoint of change from baseline of the bedtime assessment from the patient daily diary during Day 1 through Day 14 will be evaluated at a two-sided study wide alpha level of 0.05. If the primary endpoint is not statistically significant, no further formal hypothesis testing will proceed and the analyses of the secondary endpoint will be conducted as an exploratory analyses.

Exploratory endpoints will not be type I error controlled and thus, considered exploratory and hypothesis generating.

Unit of Analysis

Safety endpoints will be analyzed for both eyes. For efficacy endpoints, the unit of analysis will be the “study eye” as defined by the following:

Study Eye: Eyes are eligible for analysis if they meet all “inclusion criteria” as specified in [Section 5.3](#). In the case that both eyes are eligible for analysis, the study eye will be the eye with the largest change [REDACTED] in corneal total fluorescein staining score [REDACTED] at baseline (Visit 2). If the baseline change [REDACTED] in corneal total fluorescein staining score is the same in both eyes, then the right eye will be used as the study eye. If only one eye meets all inclusion criteria, then the single qualifying eye is the study eye.

Primary Efficacy Analysis

For the primary efficacy endpoint, change from baseline [REDACTED] will be calculated as visit – (minus) baseline [REDACTED] such that a positive difference indicates a

worsening of dry eye signs or symptoms. In addition, treatment comparisons between active and placebo will be calculated as 0.3% SI-614 – (minus) placebo, such that a negative result indicates a better score for the 0.3% SI-614 (i.e., 0.3% SI-614 demonstrated less severity in dry eye signs or symptoms than the placebo group).

The primary analysis of the primary endpoint will use the ITT population with multiple imputation methodology as specified in Estimand 1 (defined in [Section 11.4.4](#)) using Analysis of Covariance (ANCOVA) if the rate of missing data for an endpoint is balanced between the two treatment groups (as evaluated by the Fisher's exact test at an alpha level of 0.05) or the rate of missing data for an endpoint is $\leq 5\%$ in all subjects. If the rate of missing data for an endpoint is imbalanced between treatment groups (as demonstrated by the Fisher's exact test with a p-value < 0.05) and the rate of missing data for an endpoint is greater than 5% in all subjects, then the primary analyses will utilize the ITT population with observed data only using the permutation test with trimmed means methodology with Estimand 2 (defined in [Section 11.4.4](#)).¹

The ANCOVA model used to compare the change from baseline [REDACTED] to Day 29 [REDACTED] in corneal total fluorescein staining score in the study eye between 0.3% SI-614 and placebo will include baseline [REDACTED] in corneal total fluorescein staining score in the study eye at Visit 2 and treatment group as covariates.

As supportive analyses, two-sample t-tests and a Wilcoxon rank sum test will be conducted to compare the change from baseline [REDACTED] at Day 29 [REDACTED] between the two treatment groups. Additional exploratory comparisons of the mean raw scores of corneal total fluorescein staining score at Day 29 [REDACTED] and baseline [REDACTED] (Visit 2, Day 1) between the treatment groups will be conducted using two-sample t-tests and Wilcoxon rank sum tests. Quantitative summary statistics will be provided for baseline Day 1 [REDACTED], Day 29 [REDACTED], and change from baseline [REDACTED] at Day 29 [REDACTED].

Sensitivity analyses will include multiple imputation by placebo group-based pattern mixture models (PMM), multiple imputation via randomized treatment group-based Markov Chain Monte Carlo (MCMC), single imputation by Last Observation Carried Forward (LOCF), tipping point analyses, and analyses of observed data only using the ITT and PP populations.

Secondary Efficacy Analyses

Analyses of the secondary efficacy endpoint of the change from baseline (Day -7 through Day -1) in average score of ocular discomfort and dryness at the bedtime assessment from the patient daily diary during Day 1 through Day 14 will use a Mixed-Model Repeated Measures (MMRM). The model will include the baseline average score of ocular discomfort and dryness (average of Day -7 through Day -1), treatment group, study day (Day 1 to Day 14 as categorical variables), and the interaction between treatment group and study day as fixed effects with correlated errors due to study day. The overall treatment differences (0.3% SI-614 versus placebo) and the corresponding p-values will be estimated based on the MMRM. As

a sensitivity analysis, the above model will also be run without including the baseline average score of ocular discomfort and dryness symptom as a covariate.

As an additional sensitivity analysis of the average score of ocular discomfort and dryness symptom, the change from baseline in average ocular discomfort and dryness score from Day 1 to Day 14 will also be compared between the 2 treatment groups using two-sample t-tests and Wilcoxon rank sum tests for each individual day. In addition, an ANCOVA model using the baseline average score of ocular discomfort and dryness and treatment group will be used to examine change from baseline at each day.

Analyses of the secondary endpoint will utilize the ITT population using observed data only. Sensitivity analyses will include multiple imputation as described in Estimand 1, multiple imputation by placebo group-based PMM, multiple imputation via randomized treatment group-based MCMC, single imputation by LOCF, and analyses of observed data only using the PP population.

Exploratory Efficacy Analyses

Exploratory efficacy variables will generally be analyzed on the ITT population using observed data.

For signs [REDACTED] (including fluorescein staining, lissamine green staining, TFBUT, and conjunctival redness), the change [REDACTED]

[REDACTED] at each visit will be compared between the 2 treatment groups using a two-sample t-test, a Wilcoxon rank sum test, as well as an ANCOVA model adjusting for baseline [REDACTED] value. In addition, change from time point-matched baseline ([REDACTED]) will be analyzed similarly.

For symptom measures (including OSDI, [REDACTED] Ocular Discomfort and 4-symptom Questionnaire), each individual symptom score as well as the change from baseline ([REDACTED] at Visit 2) will be compared between 0.3% SI-614 and placebo for each visit using a two-sample t-test, a Wilcoxon rank sum test, and an ANCOVA model adjusting for baseline.

[REDACTED] Ocular Discomfort Scale [REDACTED] is measured every 5 minutes [REDACTED] The area under the curve will be calculated for each patient using the trapezoidal rule, and compared between treatment groups using a two-sample t-test, as well as an ANCOVA model adjusting for baseline (Visit 2 area under the curve).

Safety Variables

Frequencies and percentages of patients with treatment-emergent adverse events (TEAEs), serious TEAEs, and TEAEs causing premature discontinuation will be provided by treatment group. An AE is treatment emergent if it occurs or worsens after the first dose of study treatment. Furthermore, frequencies will be given of patients with TEAEs by system organ class (SOC), by SOC and preferred term (PT), by SOC, PT and maximal severity, by SOC, PT and strongest relationship, and by

SOC, PT, maximal severity, and strongest relationship. Separate analyses will be performed for ocular and non-ocular TEAEs.

Other safety endpoints including visual acuity, slit lamp biomicroscopy, and corneal sensitivity will be summarized by treatment group and visit using descriptive statistics. Changes or shifts from baseline will also be summarized where appropriate. For assessments performed by eye, study eye and fellow eye will be summarized separately. In addition, shifts from baseline to worst on-treatment value for ocular safety assessments will be summarized. All safety endpoints will be assessed using the Safety population.

Summary of Known and Potential Risks and Benefits to Human Patients

SI-614 ophthalmic solution appears to be safe and well-tolerated. In a Phase 2 clinical trial of SI-614 with 150 dry eye patients, a subgroup of more symptomatic dry eye patients treated with 0.3% SI-614 showed statistically significantly reduced corneal fluorescein staining and statistically significantly improved dry eye symptoms. The most common ocular TEAEs were instillation site reactions (24.7% of TEAEs), and possibly but less likely, ocular hyperemia or reduced visual acuity (each of which were 1.3% of TEAEs). In a Phase 2/3 study in 240 patients with dry eye, 0.3% SI-614 showed statistically significant improvement in the dry eye symptom primary efficacy endpoint, reproducing the results of the Phase 2 study subgroup analysis. The most frequently reported acute AE was instillation site pain: 16 patients (13.1%) in the 0.3% SI-614 group and 8 patients (6.8%) in the placebo group, and all of these events were mild in severity and were resolved by the end of the study. Overall, the incidence of TEAEs in the 0.3% SI-614 group was comparable with that in the placebo group.

Potential Risks: Phase 2 and Phase 2/3 data indicate that SI-614 has an acceptable safety profile.

Potential Benefits: Patients may experience a reduction in various signs and symptoms of dry eye disease.

TABLE OF CONTENTS

SYNOPSIS	3
TABLE OF CONTENTS	13
LIST OF ABBREVIATIONS	16
1 INTRODUCTION	17
1.1 Risks and Benefits	18
2 STUDY OBJECTIVES	20
3 CLINICAL HYPOTHESES	21
4 OVERALL STUDY DESIGN	22
5 STUDY POPULATION	24
5.1 Number of Patients	24
5.2 Study Population Characteristics.....	24
5.3 Inclusion Criteria.....	24
5.4 Exclusion Criteria.....	25
5.5 Withdrawal Criteria (if applicable)	26
6 STUDY PARAMETERS	28
6.1 Efficacy Measures	28
6.1.1 Primary Efficacy Measures.....	28
6.1.2 Secondary Efficacy Measures.....	28
6.1.3 Exploratory Efficacy Measures.....	28
6.2 Safety Measures	28
6.3 Other Measures.....	28
7 STUDY MATERIALS	29
7.1 Study Drug(s)	29
7.1.1 Run-In	29
7.1.2 Study Drug(s)/Formulation(s).....	29
7.1.3 Study Drug Packaging Configuration.....	29
7.1.4 Study Drug Storage and Accountability	29
7.1.5 Instructions for Dispensation, Use, and Administration	29
7.2 Other Study Supplies.....	30
8 STUDY METHODS AND PROCEDURES	31
8.1 Patient Entry Procedures	31
8.1.1 Overview	31
8.1.2 Informed Consent.....	31
8.1.3 Washout Intervals	31
8.1.4 Procedures for Final Study Entry.....	31
8.1.5 Methods for Assignment to Treatment Groups:	31
8.2 Concurrent Therapies	32

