5 STUDY POPULATION

5.1 Number of Patients

It is estimated that approximately 230 patients (115 in each arm) will be enrolled. Patients will be randomized in a 1:1 ratio of 0.3% SI-614 to placebo.

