11.3 Sample Size

The power and sample size for this study were calculated based on the results from the previous Phase 2 and Phase 2/3 study.

In order to have 90% power to detect a difference of -0.75 between SI-614 and placebo, 109 patients per treatment arm are required to be randomized. This assumes a two-sided test at alpha = 0.05 and a common standard deviation (SD) of 1.7 in both treatment arms.

Accounting for up to 5% dropouts in the study, 115 patients per treatment arm, or 230 total patients are required to have 90% power for the primary endpoint.

The hierarchical, secondary endpoint of the change from baseline in the average score of ocular discomfort and dryness at the bedtime assessment from the patient daily diary during Day 1 through Day 14 will have 51% power with this sample size, assuming a difference between SI-614 and placebo of -0.13. This endpoint will be tested conditional upon the primary endpoint being successful, thereby maintaining the study-wide type I error rate for both endpoints. The sample size calculation assumes a two-sided test at alpha = 0.05 and a common SD of 0.48 in both treatment arms.

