4.1 Primary Efficacy Endpoint

The primary efficacy endpoint is the following:

- Change from baseline (CFB) [REDACTED] to Day 29 [REDACTED] in total corneal fluorescein staining (tCFS) score on the [REDACTED] Scale in the study eye.
 - Fluorescein staining will be conducted at all visits, including all [REDACTED] time points.
 - Grading of the [REDACTED] region will be conducted using the [REDACTED] Corneal and Conjunctival Staining Scale, which is a 0 to 4 scale [REDACTED] and where grade 0 = No Staining and 4 = Confluent Staining.
 - The tCFS score is derived using the sum of the [REDACTED] regions such that possible scores range from 0 to 12.

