14.1 Primary Efficacy Endpoint

14.1.1 PRIMARY ANALYSIS METHODS

Primary analysis of the CFB [REDACTED] to Day 29 [REDACTED] in tCFS will be performed using an Analysis of Covariance(ANCOVA) model adjusted for baseline value with treatment group as the explanatory variable on ITT population with Estimand 1 or ITT population with Estimand 2 depending on the rate of intercurrent events. Least squares (LS) means for each treatment group and the LS mean difference comparing 0.3% SI-614 with placebo will be presented from the model together with SEs, two-sided 95% CIs, and one-sided p-values.

Subject listings will be provided for the primary efficacy endpoint for all randomized patients.

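### The primary ANCOVA is valid but adjusts for only one of the four pre-randomization staining readings an eligible study eye has; adding others would gain precision at almost no cost

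*Protocol*

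**What the plan says.** **The model.** Protocol 11.4.4 and the Synopsis describe an ANCOVA of the change to Day 29 with a baseline term "in corneal total fluorescein staining score in the study eye at Visit 2 and treatment group as covariates". SAP 14.1.1 describes a "model adjusted for baseline value with treatment group as the explanatory variable". SAP 9.3 defines the primary baseline as one pre-randomization Visit 2 measurement.

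**The readings.** Protocol 8.3.1 lists fluorescein staining twice at Visit 1 and twice at Visit 2, on either side of the in-office run-in drop and a redacted step. Randomization follows the second Visit 2 round. SAP 4.1 agrees: "Fluorescein staining will be conducted at all visits, including all" time points (label redacted). Inclusion criterion 9a (Synopsis and Protocol 5.3) asks at both visits for an increase of at least 3 "in fluorescein staining score in the cornea", which needs two readings per visit. The study eye must meet all inclusion criteria (Protocol 11.4.2, SAP 9.1).

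**Where the remaining information goes.** The Visit 2 within-visit change, cut at 3.5, is a stratification factor (Protocol 8.1.5, SAP 3.1) and helps to choose the study eye. In analyses of the primary endpoint it returns only as a stratum: in the sensitivity ANOVA of SAP 14.1.2 and the subgroup analyses of SAP 17. No analysis is described that uses the Visit 1 staining scores as covariates.

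**The concern.** A single examiner-graded score is a noisy measure of an eye's underlying staining level. Further readings of the same eye on the same scale, taken before randomization, can explain Day 29 variation that the single baseline misses. Leaving them out keeps that variation in the residual and widens the confidence interval.

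This endpoint alone decides whether the study succeeds, and it gates the secondary endpoint. By the protocol's own account, the Phase 2/3 study missed its corneal staining sign. The sponsor also treats the within-visit change as important enough to stratify on, yet the primary model does not include it.

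**Working it through.** **1. Plan's figures.** Inputs, all from Protocol 11.3 unless noted:

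- Target: "In order to have 90% power to detect a difference of -0.75 between SI-614 and placebo, 109 patients per treatment arm are required".
- Test level two-sided 0.05; SD 1.7 in each arm; allocation 1:1 (Protocol 5.1).
- Dropout allowance 5%, giving 115 per arm and 230 in all.

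Results:

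- Normal approximation: n = 2(1.960 + 1.282)² × 1.7² / 0.75² = 108 per arm.
- Noncentral t, two-sample: power is 89.7% at 108 and 90.0% at 109, so n = 109.
- Dropout: 109 / 0.95 = 114.7, rounded up to 115.

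The stated sample size is reproduced.

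**2. Cost if the added readings explain nothing.** Power uses the noncentral t with noncentrality 0.75 / (SD × √(2/n)), losing one degree of freedom per covariate. With SD 1.7, 109 per arm and four staining covariates, power is still 90.0%.

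**3. Gain under a common correlation (assumed).** Let ρ be the correlation between any two readings, including Day 29. With k readings in the model, R²(k) = kρ² / (1 + (k − 1)ρ), and the residual variance relative to the plan is (1 − R²(k)) / (1 − R²(1)). Taking 1.7 as the residual SD of the planned ANCOVA, with 109 per arm:

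| ρ | R²(1) | R²(3) | R²(4) | Variance ratio, 3 readings | Variance ratio, 4 readings | Power, 3 readings | Power, 4 readings |
|---|---|---|---|---|---|---|---|
| 0.1 | 0.010 | 0.025 | 0.031 | 0.985 | 0.979 | 90.4% | 90.6% |
| 0.3 | 0.090 | 0.169 | 0.189 | 0.913 | 0.891 | 92.4% | 93.0% |
| 0.5 | 0.250 | 0.375 | 0.400 | 0.833 | 0.800 | 94.4% | 95.2% |

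Three readings means the planned baseline plus the two covariates proposed in the fix. At ρ = 0.5 with four readings, the residual SD is 1.7 × √0.800 = 1.521, 88 per arm would give 90% power, and the confidence interval is about 11% narrower (√0.800 = 0.894).

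**4. Gain if correlation decays with time (assumed).** Take Visit 2 with Day 29 = 0.60, Visit 1 with Day 29 = 0.45, and Visit 1 with Visit 2 = 0.65. Using both readings, R² = (0.36 + 0.2025 − 2 × 0.60 × 0.45 × 0.65) / (1 − 0.4225) = 0.366. The variance ratio is 0.634 / 0.64 = 0.990, and power is about 90.3%.

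**5. Dependence on the redacted time point.** Seven structured scenarios were run, with correlations of 0.3-0.7 for the same time point at different visits, 0.1-0.5 for different time points at different visits, and 0.5-0.7 within a visit.

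- If the planned covariate matches the Day 29 time point, the other Visit 2 reading alone gives a variance ratio of 0.98-1.00. All four readings give about 0.82-0.94, so most of the gain comes from Visit 1.
- If it does not match, the second Visit 2 reading alone gives about 0.67-0.92 and all four give about 0.56-0.87.

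**6. If 1.7 is the SD of the raw change.** With equal variances, the planned residual SD is 1.7 × √((1 + ρ)/2). At ρ = 0.5 this is 1.472, and planned power is already 96.3%. With all four readings the SD is 1.472 × √0.800 = 1.317 and power is 98.7%.

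**The case against.** **Nothing is broken.** Baseline-adjusted ANCOVA is a standard choice, and no bias, type I error problem or contradiction arises from it. This stands. A reader might infer that the trial is underpowered or the model wrong; the reproduced sample size and the validity of the ANCOVA rule that out.

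**The size of the gain is assumed.** This also stands. A reader might infer a guaranteed gain of at least 5%, or power of 96%. The documents contain no correlation, and the cases with ρ = 0.1 or decaying correlation give only 1-2%. Decay is plausible: the first Visit 1 round precedes all run-in dosing, two weeks of run-in vehicle separate the visits, and selection on staining at both visits can weaken correlations. Any power gain over 90% also depends on what the 1.7 describes, which the documents do not say.

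**The information is not wholly unused.** True for the second Visit 2 reading, through stratification, the sensitivity ANOVA and the subgroups. A two-level stratum discards most of the detail, however, and it is absent from the primary model. None of this applies to Visit 1.

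**Not every randomized eye need have all four readings.** Correct. The ITT population keeps all randomized patients (SAP 8.1), and Protocol 5.5 foresees erroneous admissions. The claim is therefore limited to eligible eyes, and the fix needs a rule for missing covariates.

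**The gain may not apply.** If Estimand 2 is triggered, SAP 4.1.2 tests with a permutation test on trimmed means, and an ANCOVA gain would not carry over directly. This stands.

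**Conclusion.** The point holds as an efficiency recommendation. An eligible study eye has four pre-randomization staining readings; the primary model uses the Visit 2 baseline alone. The description of that baseline as one reading rests on SAP 9.3, since the time-point label is redacted. If the label hid a within-visit change, both Visit 2 readings would enter as one covariate and Visit 1 would still be unused.

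The assumed reduction in residual variance runs from about 0-2% to about 20%. Power at 109 per arm goes from 90% to about 90-95% if 1.7 is the ANCOVA residual SD. Otherwise planned power is already above 90% and the return is mainly a tighter interval. The balance still favours the change: if the readings add nothing the loss is negligible, and the data are already collected. It does not support calling the plan deficient.

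**What to change.** Before unmasking, specify in SAP 14.1.1, and align Protocol 11.4.4, that the primary Estimand 1 ANCOVA:

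- keeps the planned baseline and treatment terms;
- adds, as continuous covariates, the study eye's Visit 1 total corneal staining score at the time point matching the baseline, and the second Visit 2 score. With the baseline, the latter also carries the continuous information behind stratification factor 2.

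In SAP 14.1.1.1, include the same covariates in the imputation model, and impute any missing covariate value without reference to treatment. Keep the single-baseline ANCOVA as a sensitivity analysis. State that the added covariates apply to the ANCOVA and not to the Estimand 2 permutation test.

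The cost is wording in both documents and programming, with no new data. The two covariates use two degrees of freedom, or three if the remaining Visit 1 reading is also added, out of about 230 patients.
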